2.4.3.2 Compliance

A given administration will be considered noncompliant if the patient did not take the planned dose (eg, missed dose, overdose, or underdose) of treatment as required by the protocol. No imputation will be made for patients with missing or incomplete data.

Compliance is calculated as the total amount of drug actually taken by a patient divided by the total amount of drug expected to be taken multiplied by 100. The number and percentage of patients with noncompliance (missed 2 or more consecutive infusions, or missed \geq 20% of total doses in the treatment or extension period) will be provided.

Treatment compliance will be summarized descriptively as quantitative variables (number, mean, SD, median, minimum, and maximum). The percentage of patients whose compliance is <80% will be summarized.

Additional dose related non-compliance will be summarized as protocol deviations.

2.4.4 Analyses of efficacy endpoints

2.4.4.1 Analysis of primary efficacy endpoint(s)

Not applicable.

2.4.4.2 Analyses of secondary efficacy endpoints

Efficacy endpoints will be summarized with both the FA set and the efficacy analysis set. Observed measurements, changes from baseline, and changes from rebaseline (LTS-switch patients only) to each applicable study time point in 6MWT distance walked (actual and % predicted based on both Enright and Gibbons equations) and PFT parameters (actual and % predicted, supine and standing FVC, FEV1, MIP, MEP, and PEF) will be summarized using summary statistics. 95% CIs will be used to estimate the change from baseline at each study visit. Missing data will not be imputed. Spaghetti plots showing patient data over time will be presented. A listing of assistive device use during the 6MWT will be provided.

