1.2.2 Secondary objectives

The secondary objectives of the LTS13769 study are to assess if the benefits of avalglucosidase alfa are maintained and the time course of response, by examining the long-term effect of avalglucosidase alfa on pharmacodynamic (PD) and exploratory efficacy variables.

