2 STATISTICAL AND ANALYTICAL PROCEDURES

The statistical analysis and reporting will be based on all data from study TDR12857 and its extension study, LTS13769. The baseline value is defined as the last non missing value prior to first TDR12857 treatment, unless otherwise specified. The rebaseline values will be the last non-missing assessment before patients switch to 20 mg/kg dose for LTS-switch patients.

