2.1.3 Efficacy endpoints

As the primary objective of this study is to assess the long-term safety and pharmacokinetics (PK) of avalglucosidase alfa (neoGAA) in patients with Pompe disease who have previously completed TDR12857, a neoGAA study, there is no primary efficacy for this extension study. However, as part of the secondary objective, exploratory efficacy endpoints will be assessed to see if the benefits of neoGAA are maintained.

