2.4.7 Analyses of pharmacodynamic variables

Pharmacodynamic variables are described in [Section 2.1.6](#).

Descriptive statistics (including mean, SD, median, minimum, maximum, and 95% confidence intervals (CI) of changes) for both observed and change from baseline (and/or rebaseline, if specified) by study visit will be provided for quantitative parameters, by group and by each patient group/dose level, unless otherwise specified. Qualitative results that are categorical will be presented with number and percentage of patients in each category. If a linear trend in the change of a pharmacodynamic endpoint is observed, a longitudinal model may be employed to model change from baseline over time.

Muscle MRI

MRI data collected from the TDR12857 and LTS13769 studies will be summarized separately, due to the updated methods used for LTS13769. The Week 27 results from TDR12857 will be used as the LTS13769 baseline for LTS13769 study (see [Section 2.5.1](#)). Descriptive statistics will be used for quantitative parameters to summarize changes over time from baseline/rebaseline for each study. The Mercuri grading will be presented both as a categorical variable (ie, number and percentage of patients in each grade over time will be presented) and as a continuous variable (ie, number, mean, SD, median, minimum, maximum, and 95% CI will be presented at each visit). Additional summaries will be presented for the patients previously allocated to the 5 or 10 mg/kg dose groups in the TDR13857 study and switched to 20 mg/kg in the LTS13769 study (see [Section 2.5.1](#)). The number of patients with abnormally high values for any specific muscle, as indicated by a T2 of >39 ms, will be presented using descriptive statistics.

Muscle biopsy

Changes from the TDR12857 baseline over time will be used to summarize continuous variables. For qualitative measures, number and patients in each category over time will be presented.

A correlative measure comparing the biopsied muscle and its MRI counterpart will also be performed.

Urine Hex4

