2.5 DATA HANDLING CONVENTIONS

2.5.1 General conventions

Baseline is defined as the last observation prior to the first treatment in the TDR12857 study, unless otherwise specified. In addition, a rebaseline value may be used for the summaries of select assessments for patients who previously enrolled in the 5 and 10 mg/kg dose groups and switched to the 20 mg/kg dose in the LTS13769 study, in order to compare changes before and after the switch. (In some cases, assessments were not repeated at the rebaseline visit, depending on the last available assessment dates [see protocol Section 10.1.2.7]. In such circumstances, the last available assessments prior to dose switch will be used for the rebaseline values of the parameters of interest.)

Due to the centralized MRI reading procedures, there will be multiple Week 27 values, as the Week 27 image will be reread in accompany to each LTS13769 MRI read. The LTS13769 baseline will be the mean of the multiple Week 27 of the particular parameter. The previous Week 27 reads performed during the TDR12857 study will be presented in the presentation of data collected during the TDR12857 study period, but excluded in the calculation of the LTS13769 baseline, as the vendor [same vendor used for TDR12857] has upgraded their image processing capabilities.

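### For 6MWT and lung function the SAP asks whether benefit is maintained but plans no within-patient estimate, with a confidence interval, of change since the end of TDR12857

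*SAP*

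**What the plan says.** SAP 1.2.2 sets the aim to "assess if the benefits of avalglucosidase alfa are maintained and the time course of response". SAP 2.1.3 repeats it for efficacy: "exploratory efficacy endpoints will be assessed to see if the benefits of neoGAA are maintained".

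The reference for change is fixed in SAP section 2: "The baseline value is defined as the last non missing value prior to first TDR12857 treatment, unless otherwise specified". SAP 2.5.1 agrees. A second reference exists for one group: "The rebaseline values will be the last non-missing assessment before patients switch to 20 mg/kg dose for LTS-switch patients".

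For 6MWT and PFT, SAP 2.4.4.2 plans "Observed measurements, changes from baseline, and changes from rebaseline (LTS-switch patients only) to each applicable study time point in 6MWT distance walked", with the same for the PFT parameters. On intervals it says "95% CIs will be used to estimate the change from baseline at each study visit"; none is named for change from rebaseline. It also plans spaghetti plots and no imputation. SAP 2.4.4.4 lists no further efficacy analysis. Protocol 11.8 likewise names only change from baseline with a 95% CI.

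SAP 2.1.3.2 lists 6MWT and PFT at TDR12857 baseline, Week 13 and Week 25, and at roll-over. Appendix B Table 1 gives Week 25 its own analysis visit. It gives the LTS entry assessment none.

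**The concern.** Change from the pre-treatment value shows how much of the total gain remains at a visit. Maintenance is a different question: how far patients have moved from the level they had reached on treatment when they entered the extension. For that, the natural reference is the last value before the first LTS13769 infusion.

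The LTS-switch group has an on-treatment reference, its rebaseline, although that addresses the dose change and not the end of TDR12857. Patients on 20 mg/kg throughout have none. If they gained during TDR12857 and later lost part of it, the one quantity given with an interval would still have a positive mean. The size and precision of the loss would be left to the reader.

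**Working it through.** The plan states no effect size, SD, group size or maintenance margin, so there is no figure to reproduce. The check has three parts.

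**1. What each planned output offers for patients on 20 mg/kg throughout**

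- Observed values by visit, including Week 25: a decline in means is visible, with no paired estimate.
- Change from baseline with 95% CI: total effect, not movement since Week 25.
- Change from rebaseline: does not apply to them.
- Spaghetti plots: individual decline is visible, not estimated.

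**2. How the two contrasts differ**

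Let G be the mean gain at Week 25 and L the fraction later lost, with the same patients at both visits. Then:

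- mean change from baseline = G(1 - L), positive for any L below 1;
- mean change from Week 25 = -G × L;
- 95% CI = mean ± t(0.975, n-1) × SD/√n.

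Assumed for FVC: G = 5 percent-predicted points, n = 12, SD of change 6 for both contrasts. The half-width is 2.201 × 6/√12 = 3.8.

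| Loss of gain | From baseline | From Week 25 |
|---|---|---|
| 50% | +2.5 (-1.3 to 6.3) | -2.5 (-6.3 to 1.3) |
| 80% | +1.0 (-2.8 to 4.8) | -4.0 (-7.8 to -0.2) |
| 100% | 0.0 (-3.8 to 3.8) | -5.0 (-8.8 to -1.2) |
| 120% | -1.0 (-4.8 to 2.8) | -6.0 (-9.8 to -2.2) |

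Assumed for 6MWT: G = 30 m, SD 50 m, n = 12. The half-width is 2.201 × 50/√12 = 31.8 m. An 80% loss gives +6.0 m (-25.8 to 37.8) from baseline and -24.0 m (-55.8 to 7.8) from Week 25.

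**3. What can be recovered from the planned tables**

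With complete data, the later mean change minus the Week 25 mean change equals the paired mean: in the 80% FVC case, 1.0 - 5.0 = -4.0. With dropout and no imputation, the two rows come from different patients and the equality fails.

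The interval cannot be recovered in either case, because it depends on the correlation r between the two changes from baseline, which is not reported. With SD 6 at both visits and n = 12, the half-width is 2.201 × √(36 + 36 - 72r)/√12:

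- r = 0: 5.4
- r = 0.5: 3.8 (the case in the table)
- r = 0.9: 1.7

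For a mean of -4.0, that range runs from -9.4 to 1.4 at r = 0 to -5.7 to -2.3 at r = 0.9.

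**The visit window.** In Appendix B Table 1 the Week 52 window (target day 365) opens on the first day of LTS. Appendix B Table 4, for biochemistry, puts LTS entry at target day 183 with its own visit. A 6MWT or PFT value from about that day is 365 - 183 = 182 days off the Week 52 target. The closest-to-target rule drops it if a Month 6 value exists and reports it as Week 52 if none does. Protocol 10.1.1 lists no 6MWT or PFT at the LTS baseline visit, so such values may be few. Where there is none, Week 25 is the reference.

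**The case against.** The plan is descriptive and has no test, margin or rule for maintenance, so nothing is formally judged. The planned tables show Week 25 beside every later visit, and the plots show each patient. A reader might infer that maintained and partly lost benefit could not be told apart. The documents do not support that: the decline would be visible, and with complete data its mean follows by subtraction. Nor is pre-treatment the only reference, since LTS-switch patients have rebaseline changes.

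A reader might also take the MRI plan as proof that the SAP already accepts an end-of-TDR12857 reference for maintenance: "The Week 27 results from TDR12857 will be used as the LTS13769 baseline for LTS13769 study". SAP 2.4.7 and 2.5.1 tie that choice to updated methods and the vendor's upgraded image processing. It is a comparability measure and no precedent.

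The illustration needs an early gain. The only one the documents report is FVC improvement in treatment-naïve patients on 20 mg/kg, in the rationale for amendment 03 (Protocol 17.2.3). None is reported for 6MWT or for previously treated patients.

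Finally, the analysis follows Protocol 11.8, efficacy is exploratory, and the November 2023 erratum takes it out of the protocol's secondary objective.

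All of this stands and lowers the weight. It does not supply the missing interval, and the SAP still poses the maintenance question for efficacy.

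**Conclusion.** The point holds as a minor one. For 6MWT and PFT, change after the end of TDR12857 can be seen but is not estimated within patients with a confidence interval, and patients on 20 mg/kg throughout have no on-treatment reference value.

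Its numerical size is unknown. The figures above rest wholly on assumed gains, SDs, correlation and n = 12, and show only how the two contrasts can differ. A positive change from baseline hides a loss only if there was a mean gain by Week 25 and less than all of it was lost. If all of it is lost, the planned mean is zero; beyond that it is negative. The gap in the plan does not depend on those assumptions: no reported quantity fixes the interval for change since Week 25.

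**What to change.** In SAP 2.4.4.2, add for patients with both values the paired change from the last assessment before the first LTS13769 infusion (Week 25 or roll-over) to each LTS visit. Do this for 6MWT and each PFT parameter, by patient and dose group, with a t-based 95% CI and the number of pairs. Describe it as the descriptive estimate to read for maintenance, without a decision rule.

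Keep change from baseline for total effect and the rebaseline tables for LTS-switch patients. For that group the new contrast spans the dose switch at later visits, so the two should be read together.

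In Appendix B Table 1, give any pre-infusion LTS-entry assessment its own analysis visit, so that a value from the first day of LTS does not fall in the Week 52 window.

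Note in the SAP that efficacy is exploratory and no longer part of the protocol's secondary objective after the erratum. If results are already known, label the added analysis post hoc.

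The cost is a few lines of SAP text, one more column per efficacy table and one more visit window. No new assessment is needed.

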11.7 PHARMACODYNAMIC AND EXPLORATORY BIOMARKER ANALYSIS

Pharmacodynamic endpoints as described in [Section 9.3](#) will be summarized using descriptive statistics at each scheduled study visit. Observed measurements, as well as change from baseline, will be summarized. If a linear trend in the change of a pharmacodynamic endpoint is observed, longitudinal model may be employed to model change from baseline over time. In addition, 95% confidence intervals (CI) of changes will be presented.

Evaluation of intact muscle and fatty replacement from MRI will be descriptive using a grading scale and, if feasible, quantitative using a numeric method of determining the degree (%) of overall fatty replacement of muscle from the skeletal muscle MRI and an individual (%) measure for the quadriceps. A correlative measure comparing the biopsied muscle and its MRI counterpart will also be performed.

Urine Hex4 levels will be summarized using descriptive statistics at each scheduled study visit. Observed measurements, as well as change from baseline, will be summarized. If a linear trend in the change of urine Hex4 levels is observed, a longitudinal model may be employed to model change from baseline over time. In addition, 95% CIs of changes will be presented. Due to the small number of patients, nonlinear relationship will not be formally characterized.

To explore the relationship between PK endpoints and urine Hex4 levels, scatter plots and linear mixed model may be used as appropriate.

To explore the relationship between glycogen content and biomarkers, correlational statistics (Spearman or Pearson) at each scheduled study visit will be used. In addition, scatter plots and linear regression analysis will be used to describe the relationship between glycogen content and each biomarker.

Similar analyses will be carried out to explore the relationship between other pharmacodynamic endpoints, exploratory biomarkers, and exploratory efficacy assessments.

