11.8 EXPLORATORY EFFICACY ANALYSIS

Observed measurements and changes from baseline to each study time point in 6MWT distance walked and PFT parameters (% predicted sitting and supine FVC, FEV1, MIP, MEP, and PEF) will be summarized using summary statistics. In addition, 95% CIs will be used to estimate the change from baseline at each study visit. Graphical displays showing data over time will be presented.

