2.1.3.2 Secondary efficacy endpoint(s)

The exploratory efficacy endpoints include the six-minute walk test (6MWT) and the pulmonary function testing (PFT). These assessments were performed at baseline, Week 13, and Week 25 in the TDR12857 study, at the baseline for roll over to LTS 13769, and performed every 6 months, at the rebaseline visit (for patients previously in the 5 and 10 mg/kg dose groups only; see [Section 1.4](#)), and at the end of study visit in the LTS13769 study.

Six-minute walk test (6MWT)

The 6MWT assessments include: the distance walked in 6 minutes, measured in meters; the percentage of predicted distance; and the amount of time walked to quantify endurance (as all patients may not complete the full 6-minute walk). In addition, data will be collected for pretest versus posttest changes in heart rate and assistive device use. The distance (in meters) will be recorded and the corresponding percentage of predicted value will be calculated. The percentage of predicted distance walked will be calculated based on the normal reference equation in [Table 1](#). For analysis purposes, the age at each assessment will be calculated based on (assessment date - birth date + 1)/365.25.

Table 1 - Equations for calculating reference value for percentage of predicted total distance walked in 6MWT (1)

Age at baseline	Gender	Equation
≥18 years	Male and Female	868.8 - 2.99 * age - 74.7 * sex

Age in years; sex = 0 if male and sex = 1 if female.

In order to compare the percent predicted values with studies using several percent predicted equations, the percentage of predicted distance walked will be calculated based on the normal reference equation in [Table 2](#). For analysis purposes, the age at each assessment will be calculated based on (assessment date - birth date + 1)/365.25, weight is collected at the time of the assessment and height will be baseline height for the study.

Table 2 - Equations for calculating reference value for percentage of predicted total distance walked in 6MWT (2)

Gender	Equation
Male	7.57*height (cm)-5.02*age (year)-1.76*weight (kg)-309
Female	2.11*height (cm)-5.78*age (year)-2.29*weight (kg)+667

Additional supportive analysis of 6MWT based on subjects who completed the full 6 minute walk by excluding subjects that walked less than 6 minutes will be provided.

Pulmonary function test

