2.5.3 Missing data

No imputation (single or multiple) is planned for this study.

For categorical variables, patients with missing data are not included in calculations of percentages unless otherwise specified. When relevant, the number and percentage of patients with missing data is presented.

Handling of computation of treatment duration if investigational medicinal product end of treatment date is missing

For the calculation of the treatment duration, the date of the last dose of IMP is equal to the date of last administration reported on the end-of-treatment CRF page. If this date is missing, the exposure duration should be left as missing.

The last dose intake should be clearly identified in the CRF and should not be approximated by the last returned package date.

Handling of medication missing/partial dates

No imputation of medication start/end dates or times will be performed. If a medication date or time is missing or partially missing and it cannot be determined whether it was taken prior or concomitantly, it will be considered a prior, concomitant, and posttreatment medication.

Handling of adverse events with missing or partial date/time of onset

Missing or partial adverse event onset dates and times will be imputed so that if the partial adverse event onset date/time information does not indicate that the adverse event started prior to treatment or after the treatment-emergent adverse event period, the adverse event will be classified as treatment-emergent. No imputation of adverse event end dates/times will be performed. These data imputations are for categorization purpose only and will not be used in listings. No imputation is planned for date/time of adverse event resolution.

Handling of adverse events when date and time of first investigational medicinal product administration is missing

When the date and time of the first IMP administration is missing, all adverse events that occurred on or after the day of randomization should be considered as treatment-emergent adverse events. The exposure duration should be kept as missing.

The last dose intake should be clearly identified in the CRF and should not be approximated by the last returned package date.

Handling of missing assessment of relationship of adverse events to investigational medicinal product

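### 6MWT and PFT change over 6 years is estimated only by observed-case visit means, which would overstate maintenance if declining patients leave

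*SAP*

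**What the plan says.** SAP 2.1.3 sets the question: "exploratory efficacy endpoints will be assessed to see if the benefits of neoGAA are maintained". SAP 1.2.2 adds the time course of response.

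SAP 2.4.4.2 gives the whole plan for 6MWT and PFT over time. Observed values, changes from baseline and (for LTS-switch patients) changes from rebaseline are summarised at each visit, in both the full analysis set and the efficacy set. It states "Missing data will not be imputed" and "Spaghetti plots showing patient data over time will be presented". Protocol 11.8 matches: "95% CIs will be used to estimate the change from baseline at each study visit".

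Nearby sections add no other method for change over time. SAP 2.4.4.4 (additional efficacy analyses) is marked not applicable, SAP 2.5.2 (data handling for these variables) reads none, and SAP 2.5.3 states "No imputation (single or multiple) is planned for this study". SAP 2.1.3.2 has one supportive 6MWT analysis, in which results "excluding subjects that walked less than 6 minutes will be provided". The correlations with antibody measures in SAP 2.4.5.6 do not estimate a time course.

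For pharmacodynamic endpoints, SAP 2.4.7 says that if a linear trend is seen, "a longitudinal model may be employed to model change from baseline over time". Protocol 11.7 says the same. Neither document extends this to 6MWT or PFT.

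**The concern.** Whether benefit is maintained is a question about change within patients. A by-visit mean describes only those still attending. As the group shrinks, the mean can stay level because the patients who are getting worse have gone. The visit-wise CI does not show this, because it measures sampling error among the remaining patients.

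Three features of the design make this worth guarding against. Change is measured from the TDR12857 baseline, but extension visits include only the TDR12857 patients who consented to continue (SAP 1.3), so selection can begin before the first extension visit. The supportive 6MWT analysis selects further on function. And SAP 2.4.7 itself describes the number of patients as small, so a few departures can move a late mean.

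At stake is how the late 6MWT and PFT results are read. No test or decision rule depends on them.

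**Working it through.** The plan gives no sample size, SD, effect size or dropout rate for these endpoints, so there is no figure to reproduce. What follows uses assumed values throughout.

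**Data available to a model.** From SAP Appendix B, Table 1: baseline, Weeks 13 and 25 of TDR12857, and 12 half-yearly extension visits (Months 6 to 72). That is 1 + 2 + 12 = 15 scheduled measurements per patient, 14 of them post-baseline.

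**Closed form.** Suppose a fraction d leaves, namely those lowest on a normal score that has correlation rho with the change. The observed-case mean is then too high by rho × phi(z_d)/(1 - d), in SDs of change. For d = 40%, phi(z_d) = 0.386 and 0.386/0.60 = 0.64.

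| Dropout d | rho = 0 | rho = 0.5 | rho = 1 |
|---|---|---|---|
| 10% | 0 | 0.10 | 0.20 |
| 20% | 0 | 0.18 | 0.35 |
| 30% | 0 | 0.25 | 0.50 |
| 40% | 0 | 0.32 | 0.64 |

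**Simulation.** Assumed: 12 half-yearly visits, mean slope -5 m/year (6 × -5 = -30 m at year 6), between-patient slope SD 12 m/year, residual SD 25 m, and dropout hazard depending on the last observed change. Coverage is for the year-6 95% CI with 20 patients at the start. The mixed model had a random slope and was fitted to 800 patients, three times per scenario (Monte Carlo SD 1.5 to 4.8 m).

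| Dropout and decline | Dropout by year 6 | Observed-case mean (m) | CI coverage | Mixed model (m) |
|---|---|---|---|---|
| Unrelated | 18% | -30.4 | 0.95 | -29.8 |
| Unrelated | 33% | -29.7 | 0.95 | -31.1 |
| Moderate | 17% | -22.9 | 0.94 | -27.7 |
| Moderate | 35% | -14.5 | 0.91 | -28.5 |
| Strong | 25% | -12.8 | 0.85 | -30.0 |
| Strong | 39% | -2.8 | 0.76 | -33.3 |

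The upward bias in the last four rows is 7.1, 15.5, 17.2 and 27.2 m (observed-case mean minus -30).

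**What small numbers do alone.** Under these assumptions the SD of the year-6 change is √((12 × 6)² + 25²) = √5809 = 76 m. With 20 patients the standard error is 76/√20 = 17 m and the CI half-width about 2.09 × 17 = 36 m, wider than the 30 m decline. The simulated CI accordingly failed to show a decline in 59-63% of runs with complete data, 69-73% under unrelated dropout and 79-96% under decline-related dropout.

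**Shape of the time course.** The mixed model above had the right shape by construction. With an assumed plateau followed by decline to a true -40 m, a single-slope model gave -25 to -29 m, and was wrong even when dropout was unrelated to decline. Mixed models with time as visit category or piecewise gave -40 to -42 m. Observed-case means ran from -40 m to -11 m. A separate run (24 patients, slope SD 10 m/year, residual SD 25 m, gain held to year 3 and then decline to -40 m) gave -42 m observed-case and -30 m single-slope with complete data. At 72% retained these were -24 and -25 m.

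**The case against.** A reader might infer that the plan does bias the answer toward maintained benefit. The documents do not support that. They give no dropout rate and no link between leaving and decline, and they foresee exits that need have nothing to do with function: entry to another study or commercial enzyme replacement (Protocol 9.1.1) and termination by the sponsor (Protocol 6.2.1). Under unrelated dropout the observed-case means are sound.

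Nor are visit means all that is shown. Individual plots display each truncated course, and SAP 2.2 tabulates reasons for not completing treatment. Patients who stop treatment are to stay in follow-up (Protocol 10.3.4), and those leaving early should have an end-of-study visit with 6MWT and PFT (Protocol 1.2.1 footnote b and 10.1.3.7). This limits missing data but does not close the gap: one such visit fills one analysis window and later windows stay empty. The plots yield no corrected estimate. The commitment in Protocol 10.3.5 on patients lost to follow-up covers primary endpoints only, which are safety.

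Status matters too. The November 2023 erratum removes exploratory efficacy from the secondary objective, so the maintenance question there now concerns pharmacodynamics. The SAP, signed in March 2020, still poses it for efficacy. The pharmacodynamic model is itself conditional and optional, so the contrast with 6MWT and PFT shows that such a model was thought feasible, not that one was owed here.

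Finally, the metre figures follow from assumed inputs, a model generated and fitted with the same straight-line shape was bound to recover the truth, and small numbers limit the late visits even with complete data. All of this stands. It limits the size of the claim and rules out a straight-line remedy, but it does not supply the missing sensitivity analysis.

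**Conclusion.** The concern holds conditionally. No planned estimate of 6MWT or PFT change over time draws on the earlier results of patients who have left, and no sensitivity analysis examines their absence. If decline makes leaving more likely, late-visit means overstate maintenance: by 0.10 to 0.32 SD of change at 10% to 40% dropout with correlation 0.5, and by about 7 to 27 m in the simulated decline-related scenarios. If leaving is unrelated to decline, there is no material bias. Every dropout rate, slope and SD here is assumed, so these figures illustrate direction and possible scale and do not predict this study's bias. Given the exploratory status and the absence of any test, this is a cheap improvement and does not undermine the study's safety conclusions.

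**What to change.** Keep the observed-case tables. Add one paragraph to SAP 2.4.4.2 specifying, as an exploratory sensitivity analysis for 6MWT distance and FVC % predicted:

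- A likelihood-based mixed model on all post-baseline values, with time as visit category, or piecewise with a change at rebaseline for LTS-switch patients. Do not use a single linear slope.
- A simple covariance, such as random intercept and slope, with a stated fallback if it does not converge.
- Modelled change at yearly visits with 95% CIs, printed beside the observed-case values.
- Individual plots marked by last visit attended and reason for leaving.

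The cost is that paragraph and modest programming; no new data are needed. The model assumes that dropout is explained by observed values, so it does not protect against dropout driven by unrecorded decline. With few patients, groups may have to be pooled with a group term. If the database is already locked, label the analysis post hoc.
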